**PROTOCOL**  
**"Quitting Using Intensive Treatment Study (QUITS)"**  
 PI: [name] and [name] ; UW-CTRI Grant:

**Smoking Outcome Measures:** As per Society for Research on Nicotine and Tobacco recommendations, we will analyze abstinence at 52 weeks (primary) and 23 weeks using two abstinence measures to enhance scientific rigor: (1) 7-day point-prevalence (CO-confirmed self-report of abstinence from smoking for 7 days before and including the follow-up day: CO cutoff ≤ 5ppm) and (2) prolonged (a continuous abstinence measure that ignores smoking in the first

**Table 2. Schedule of Study Activities**

	Pre-Cessation	Treatment Phase						Phone Follow-up				
		V1	C1	V2	V3	C2	C3	C4	C5	C6 	C7	C8 
Week	Orientation	Wk - 2	-1	TQD	2	4	8	11	17	23	39	52
Screening & Informed consent	X											
Randomization	X											
Pre-cessation counseling		X	X									
Cessation counseling				X	X	X	X					
Exhaled CO	X	X		X	X					X 		X 
Short questionnaire on CO exposure	X	X		X	X					X 		X 
Smoking status	X	X	X	X	X	X	X	X	X	X	X	X
Blood sample for DNA/RNA and cotinine		X										
Non-cigarette nicotine use	X	X		X		X	X			X		X
Baseline questionnaires	X	X										
IVR assessments	X	X	X	X	X							
Treatment mechanisms assessment 		X	X	X	X	X	X	X	X	X	X	X
Medication provision		X		X			X					
Medication use assessment			X	X	X	X	X	X	X	X	X 	
Adverse events			X	X	X	X	X	X	X	X	X	X

If participants claim abstinence during this assessment call, they will be invited to an in-person visit to provide biochemical verification of abstinence (CO assessment).

Treatment mechanisms include withdrawal, affect, fatigue, cigarette liking/effects, stressors, cue exposure, motivation, and self-efficacy.

Timeline follow back only

week post-quit). Per our intention-to-treat data analysis plan, any randomized smoker who does not provide biochemically confirmed evidence of abstinence will be counted as a smoker; multiple imputation also will be performed in secondary analyses to further enhance scientific rigor. A daily smoking calendar will permit determination of lapse/relapse latencies for survival and milestones analyses. In order to enhance *scientific transparency*, we will post all assessment instruments and, ultimately, de-identified data, online (e.g., the UW-CTRI website; average of 7,000 hits/month over last year from 17,387 visitors), so that other researchers can use our de-identified data and instruments (see detail in Data Sharing Plan).

## Interventions

**Pharmacotherapy:** Pharmacotherapies will be V-only (with placebo Patch) and V+P. As in the successful Koegelenberg trial, we will start NRT therapy (for both placebo and active P) 2 weeks prior to the target quit date (TQD). The V lead-in will start 1 week prior to the TQD. Table 3 displays the dosing information for the relevant experimental conditions. To enhance scientific rigor, placebo medication will be used to double-blind medication assignment. Thus, V-only condition participants will be given placebo patch. Also, 12 week duration condition participants will receive placebo medication week 13 through 23 (pill) /24 (patch) to match the 24 week duration condition participants' active medication regimen. Therefore, each participant will be given both medications for 6 months so that the number of medications provided and medication duration will not signal assignment; use instructions will be the same for placebo products as for the respective active medication (see Table 3 note).

**Table 3. Medication Dosing Regimens for the Factorial Experiment**

	Pre-Cessation Meds	Cessation Meds: 12 Weeks Duration	Cessation Meds: 24 Weeks Duration
Varenicline Pills	Days -7 to -5: 0.5 mg pill QD Days -4 to -1: 0.5 mg pill BID	Days 1 to Week 11: 1 mg pill BID Weeks 12-23: placebo pill BID	Weeks 1 to 23: 1 mg pill BID
Active Patch	Days -14 to TQD: 14 mg patch 14 mg patch	Weeks 1 to 12: 14 mg patch Week 13-24: placebo patch	Weeks 1 to 24: 14 mg patch

Note: The timing and dose adjustments for active nicotine patch shown above will be matched with the placebo patch given to the V-only condition. Also, medications may be discontinued or doses may be reduced in the case of adverse events.

Participants will receive medications and use instructions at Visit 1 and 2 and following the Week 8 call (via the mail: Table 2). Participants will be given an information sheet with medication instructions and a number to call with questions or to report concerning side effects or toxicity. Adverse events will be assessed at each person-to-person study contact during the treatment phase. Medication use will be assessed during each study contact during the treatment phase.

**Counseling:** Participants will receive counseling based on our recent factorial research and on Guideline recommendations. Pre-cessation counseling will occur at Visit 1 and Call 1 (3- and 1-week pre-TQD: Table 2). Counseling in these sessions will include instructions for using the medications with a special focus on smoking reduction, clear smoking reduction goals, and behavioral training to facilitate smoking reduction. Recent research suggests the value of combining precessation medication and reduction counseling. Cessation counseling will occur during Visits 3 & 4 and Calls 2 & 3 (Table 2) and will provide support, inculcate coping skills, promote motivation for quitting, and provide clear instructions regarding proper medication use. The medication adherence training will include elements that yielded promising effects in our prior research (e.g., data-based feedback on medication use, problem solving regarding adherence challenges, and motivational intervention to support medication

use). All counseling sessions will last about 15 min. Most counseling will occur close to the target quit day since some research suggests that such early counseling may be especially effective, and because most relapse occurs early in a quit attempt. We have a long history of successfully conducting such interventions and have existing counseling manuals that will require only modest adaptations for this work. Counselors will be bachelor-level health educators supervised by licensed psychologists. To support the scientific rigor of the work, quality/fidelity assurance strategies developed in our prior work will include intensive training in counseling techniques and ethical conduct (20 hours over 2 weeks), practice sessions, regular supervision using audio recordings of session, and quarterly team meetings to discuss safety, confidentiality, and counseling fidelity. Participants will be paired with a single counselor for all treatment contacts. The timeline for the conduct of the experiment is depicted in Figure 1.

### **Promoting Continued Experimental Participation**

We will utilize participant retention strategies that were effective in our prior research, including strategies such as scheduling flexibility, calling participants' cell phones if they request that, continued interaction with the same health counselor, and providing medication contingent upon visit attendance/call completion. If participants appear to have dropped out of the study (they miss appointments and do not reschedule, or they do not answer our phone calls, but they have not formally withdrawn from the study), we may write them (via standard mail or email) to encourage their renewed participation. Finally, consented participants who we are not able to reach using contact information obtained at the baseline and subsequent visits, we will call and/or send a letter to the alternate contacts provided by the participant, designated as a contact for this specific situation.

**Compensation:** Participants will be paid for: attending the Orientation Visit) and Visit 1 (\$20/visit), completing the follow-up calls for Weeks 4, 8, 11, 17, and 39 (\$10/call) and Weeks 23 & 52 (\$20 at Wk23, \$60 at Wk52), and for attending the two in-person follow-up visits for biochemical confirmation of abstinence, if needed (\$40 at Wk23; \$200 at Wk 52). If participants are unable to be reached for their follow-up calls at Weeks 23 and 52, they will be mailed a questionnaire that assesses their current smoking status and asked to complete and return it. Those who return the Week 23 mailed questionnaire will receive \$20 and those who return the Week 52 mailed questionnaire will receive \$40. All participants will receive \$50 if they complete at least 80% (26) of the nightly IVR assessments (this means answering at least 1 question) or \$25 if they answer between 60 and 79% of assessments (20-25 assessments). This would result in a total potential compensation of \$460. Checks will be issued after Visit 1 (up to \$40), after Week 4 (up to \$60), after Week 23 (up to \$50), after Week 52 (up to \$70) and at the Week 23 and Week 52 visits, if they are invited (\$40 at Wk23; \$200 at Wk52).

**Update:** Due to COVID-19 pandemic, participants will not be brought in for Week 52 in-person visits for biochemical confirmation of abstinence. Regardless, participants eligible for that visit will receive the full \$200 payment, as described above.

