**Specific Aim 1:** To determine whether varenicline pharmacotherapy is enhanced by either a nicotine replacement adjuvant (i.e., patch NRT) or extended medication duration (i.e., 24 vs. 12 weeks postquit). The effects of these pharmacotherapy strategies will be reflected in main effects for both experimental factors, and in direct comparisons of the enhanced varenicline conditions with standard 12-week varenicline-only. The primary outcome will be 52-week biochemically confirmed smoking abstinence (7-day point-prevalence).

**Specific Aim 2:** To determine the effects of the varenicline conditions on additional critical outcomes such as 23-week point prevalence and prolonged abstinence, smoking cessation milestones (abstinence, latency to lapse, and lapse-relapse latency), cost-effectiveness, withdrawal severity, and adverse events. The variables that mediate and moderate (e.g., genotype) the effects of the different pharmacotherapies will also be identified.

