**Phone Follow-Up Assessments:** These person-to-person phone assessments will occur at 4, 8, 11, 17, 23, 39, and 52 weeks post-TQD (Table 2). Data will be gathered on daily smoking, new quit attempts, use of other cessation medication, potential mediators (e.g., withdrawal, affect, cigarette liking/effects, stressors, cue exposure, motivation), use of any nicotine product, medication use, and adverse events. Participants claiming abstinence at the 6- and 12-month calls will be invited to a visit for biochemical testing and short questionnaire on CO exposure to confirm abstinence self-report via exhaled CO. If participants claim abstinence from cigarettes but blow a 6 or greater on the CO breath test at the Week 52 Follow-Up Visit, we will ask the participant if they will give us a saliva sample to test for cotinine. This will allow us to be more certain that these participants have not been smoking cigarettes (as evidenced by cotinine-free saliva or saliva with low levels of cotinine). At the 12-month call all participants will be asked to estimate the likelihood that their pill and their lozenge contained active medication.

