### **Analytic Approach**

**Cessation:** The primary outcome (biochemically confirmed, self-reported point-prevalence abstinence at 52 weeks post-TQD) will be analyzed via two strategies. First, we will conduct factorial design analyses using logistic regression with dummy coding that examines

PROTOCOL  
“Quitting Using Intensive Treatment Study (QUITS)”  
PI: [name] and [name] ; UW-CTRI Grant:

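### The COVID-19 update cancels the Week 52 confirmation visits but leaves the confirmed-abstinence outcome and the unconfirmed-equals-smoker rule in place, so abstainers reached after the cancellation are scored as smokers

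*Combined protocol and SAP*

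**What the plan says.** Four parts of the combined protocol and SAP bear on this.

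- **Outcome.** Specific Aim 1: "The primary outcome will be 52-week biochemically confirmed smoking abstinence (7-day point-prevalence". Smoking Outcome Measures makes the test exhaled CO with a 5 ppm cutoff: "CO-confirmed self-report of abstinence from smoking for 7 days before and including the follow-up day". Analytic Approach, Cessation, repeats the requirement: "The primary outcome (biochemically confirmed, self-reported point-prevalence abstinence at 52 weeks post-TQD".
- **Scoring.** The Smoking Outcome Measures text that continues after Table 2: "any randomized smoker who does not provide biochemically confirmed evidence of abstinence will be counted as a smoker". No exception is written. Analytic Approach, Cessation, adds that missing is taken as smoking. It supplements this with multiple imputation and unspecified sensitivity analyses.
- **Route to confirmation.** Table 2, footnote 1, says of those who claim abstinence on the Week 23 or Week 52 call: "they will be invited to an in-person visit to provide biochemical verification of abstinence (CO assessment". Under Phone Follow-Up Assessments, saliva cotinine is requested only from people who claim abstinence but "blow a 6 or greater on the CO breath test at the Week 52 Follow-Up Visit".
- **Update.** Under Compensation: "Due to COVID-19 pandemic, participants will not be brought in for Week 52 in-person visits for biochemical confirmation of abstinence". The rest of the Update deals only with paying the $200 anyway. It gives no start date, remote test or scoring rule.

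**The concern.** The primary endpoint needs a test that the study has stopped offering. Scoring missing as smoking is usually justified because a participant's failure to respond or attend suggests relapse. That reasoning does not apply here: the participant answered the call and reported abstinence, and the study cancelled the visit. The absence of a CO value then says nothing about smoking.

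At stake are the absolute quit rates at Week 52, the risk differences, the odds ratios from the planned logistic models, the power of the main-effect tests, and the cost per quit in the cost-effectiveness aim.

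**Working it through.** **1. Does anything in the text resolve the conflict?** The Week 52 CO test takes place at the cancelled visit. The saliva back-up follows a high CO at that same visit, so it is lost too. Multiple imputation is placed in secondary analyses, and its one stated assumption, that 80% of dropouts return to smoking, concerns dropouts rather than people reached by phone. The sensitivity analyses have no content. Nothing changes the primary scoring.

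**2. Inputs.** From Table 4, predicted confirmed abstinence is 29.5% versus 38.5% for Duration (12 versus 24 weeks), 28.5% versus 39.4% for patch (without versus with), and 25.0% versus 44.9% for 12-week varenicline alone versus 24-week varenicline plus patch. From Statistical Power: two-sided .05, 625 per level for main effects and 312 per arm for the last contrast. Assumed, because the documents do not give it: f, the share of otherwise confirmable Week 52 abstainers whose visit was cancelled, equal in all arms.

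**3. The plan's own power.** Two-proportion normal approximation with pooled null variance:

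power ≈ Φ[(d − 1.96·s0)/s1], where s0 = √(2·p̄(1−p̄)/n) and s1 = √((p1(1−p1)+p2(1−p2))/n).

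For Duration, d = .090, s0 = .0268 and s1 = .0267, giving .920. The plan states .88. Continuity-corrected, Fisher, unpooled, log-odds and effect-coded versions give .91 to .92, and none gives .88. Patch gives .983 (stated .97). The 24-week combination contrast gives above .99, as stated. The Duration figure therefore does not reproduce; the stated value is the more cautious one. The point does not depend on it, but the results in step 4 should be read as losses relative to f = 0.

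**4. Written rule.** Each rate p becomes p(1−f). At f = 20%, Duration is 23.6% versus 30.8%, so d = .072, s0 = .0252, s1 = .0251 and power is .817. The risk ratio stays at .385/.295 = 1.31 for every f.

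| f | Overall abstinence | Duration difference (points) | Duration odds ratio | Duration power | Patch power | Combination contrast power | Cost per quit |
|---|---|---|---|---|---|---|---|
| 0% | 34.0% | 9.0 | 1.50 | .92 | .98 | >.99 | ×1.00 |
| 5% | 32.3% | 8.6 | 1.48 | .90 | .98 | >.99 | ×1.05 |
| 10% | 30.6% | 8.1 | 1.47 | .88 | .97 | >.99 | ×1.11 |
| 20% | 27.2% | 7.2 | 1.44 | .82 | .93 | >.99 | ×1.25 |
| 50% | 17.0% | 4.5 | 1.38 | .56 | .73 | .91 | ×2.00 |

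**5. Two alternatives.** Restricting to participants whose Week 52 preceded the cancellation keeps p and reduces n to 625(1−f). Duration power is .91, .89, .85 and .66 at f = 5, 10, 20 and 50%.

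With self-report for the affected share, the main risk is over-reporting that differs by arm. Take a true rate of 34% at both levels, f = 50%, over-reporting of 10% versus 20%, and everyone giving a status. The observed rates are .34 + .5·.10·.66 = .373 and .34 + .5·.20·.66 = .406, and a nominal 5% test rejects about 22% of the time. If only 80% of non-abstainers give a status, it rejects about 16% of the time. This formula treats Table 4's confirmed rates as true abstinence. It leaves out true abstainers who would not have attended a visit but would count under self-report.

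**The case against.** The strongest reply is that the rule is conventional, conservative and balanced. With concurrent randomization and blinding, the cancellation should fall about equally on all arms, so type I error and risk ratios hold. The written rule also avoids the over-reporting risk of self-report. That stands, and it limits the harm to attenuation and lost power. It does not make the scored outcome abstinence for the people affected.

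The size is also unknown. At f = 5% the loss is small, and the combination contrast keeps power above .99 up to f = 20%. That stands too; the case rests on the text.

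A reader might infer several stronger things that the documents do not support:

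- That scoring after the cancellation is undefined. It is defined: the smoker rule has no exception and gives a determinate, though uninformative, answer.
- That the rule favours one arm or produces false claims of benefit. Nothing ties calendar timing to arm.
- That Week 23 confirmation is affected. The Update names only Week 52.
- That mailed replies are part of the same gap. For participants not reached by phone, the plan says "they will be mailed a questionnaire that assesses their current smoking status and asked to complete and return it". That is a separate matter, and an unconfirmed mailed reply is already a smoker under the written rule.

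**Conclusion.** The plan is wrong as written. The Update and the outcome and scoring text cannot both stand if the primary outcome is to measure abstinence in everyone reached at Week 52. Confidence is high for the contradiction and does not extend to its size, because the cancellation date and the number affected are not given. If f is the same in every arm, rates and risk differences fall to (1−f) of their value. Duration power falls from .92 to .88, .82 and .56 at f = 10, 20 and 50%, to be read as relative loss only. The supplementary imputation and sensitivity analyses do not cure this, since they leave the primary scoring unchanged. The documents do not single out one replacement rule. What is required is that one be named before unblinding.

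**What to change.** Before unblinding, amend Phone Follow-Up Assessments, Table 2 with the Smoking Outcome Measures text, and Analytic Approach, Cessation, so that a Week 52 confirmation cancelled by the study is not scored as smoking. Name one primary rule. The options are:

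- self-reported seven-day status from the Week 52 contact, for affected participants;
- the confirmed outcome, restricted to participants whose Week 52 preceded the cancellation;
- confirmation imputed from the pre-cancellation confirmation rate.

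Keep missing as smoking for anyone with no Week 52 status. State the cancellation date and the overall number affected. Run the rules not chosen, and the present unconfirmed-equals-smoker rule, as sensitivity analyses, with a range of over-reporting rates that includes rates differing by arm. If unblinding has already happened, label the choice post hoc and report all versions.

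The cost is a short amendment and a few extra analyses. Each option has a price:

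- Self-report mixes confirmed and unverified outcomes by calendar period, counts some true abstainers who would not have attended, and is open to the false-positive risk in the working, although blinding makes differential over-reporting less likely.
- Restriction loses power.
- Imputation assumes that the earlier confirmation rate still holds.

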### **Analytic Approach**

**Cessation:** The primary outcome (biochemically confirmed, self-reported point-prevalence abstinence at 52 weeks post-TQD) will be analyzed via two strategies. First, we will conduct factorial design analyses using logistic regression with dummy coding that examines

PROTOCOL  
“Quitting Using Intensive Treatment Study (QUITS)”  
PI: [name] and [name] ; UW-CTRI Grant:

the main and interactive effects of the two factors. Importantly, main effects obtained with dummy coding in 2-factor designs are directly interpretable even in the presence of a significant interaction as long as the interaction effect is included in the model. Thus, main effects will reflect the effects of V+P vs. V-alone, and the effects of 24- vs. 12-week treatment duration. Interaction effects would reveal whether the magnitude of differences in effects of the levels of V treatment varies in a multiplicative manner depending on duration. While we hypothesize that we will see only main effects in this research, interactions would be interpreted via visual inspection (the highest and lowest scores for the interacting treatment combinations should be readily apparent) and via simple effects tests. Second, we will conduct analyses typical of an RCT, which use logistic regression models with dummy coding to contrast each of the three enhanced varenicline treatments (12-week V+P, 24-week V-only and 24-week V+P) with the standard V-based treatment (12-week V-only). The V-only condition will serve as the reference condition because the intent is to determine if any of the enhanced V-based treatments is superior to that condition. Covariates will include sex, race, treatment site, and level of tobacco dependence (FTND item 1). Results will be reported with and without covariate adjustment and the specific effects of sex and race on each outcome will be explored. The same analytic approach will be used for secondary abstinence analyses (e.g., point-prevalence at 6-months and prolonged abstinence). The intent-to-treat principle with the assumption of missing-smoking will be used for abstinence analyses but will be supplemented with sensitivity analyses and multiple imputation for missing data to support scientific rigor. The latter models will assume that 80% of dropouts return to smoking and that abstinence likelihood is related to baseline smoker covariates. Analyses of secondary abstinence outcomes will support scientific rigor by controlling for experiment-wise error in families of related tests. Milestones analyses will be conducted as in our prior research. For instance, latency between initial abstinence and lapsing, and latency between lapsing and relapse, will be computed with Cox proportional hazards regression/survival models.

***Mediation and Moderation:*** Candidate mediators of cessation treatment effects, gathered from IVR and follow-up phone assessments will be: medication use and side effects, withdrawal symptoms (e.g., craving, negative affect, anhedonia), anticipatory pleasure from smoking, adverse events, nicotine reward, nicotine anticipation, and reports of cue-elicited urges. Treatment will be modeled both as main effects and as contrasts of particular Adjuvant X Duration combinations that differ significantly in abstinence rate from the standard V treatment condition at follow-up. Mediation will be tested using multiple indices including the joint significance test. Care will be taken to preserve mediator/outcome temporal priority and the occurrence of smoking during the quit attempt will be statistically controlled. Mediation models including multiple mediators will use methods developed for use with dynamic mediator assessments (maximum likelihood estimation using hierarchical linear modeling: HLM 5.04101). Both 23- and 52-week abstinence will be used as outcomes, which will be modeled via a weighted least squares approach in Mplus. The 23-week outcome may be more sensitive to treatment mediation than the 52-week outcome. We will attempt to characterize orthogonal routes to outcome change via use of multiple covariates and models of multiple mediation. In these models, the individual mediators revealed as strongest in univariable analyses will be included in multi-mediator models as per our prior research.

Analysis of moderators of abstinence outcomes will use both logistic regression with model-fitting techniques and regression tree analyses that reflect differential treatment responses in 23- and 52-week abstinence. The logistic regression and regression tree approaches are complementary since the former fits interactions in the entire sample whereas

PROTOCOL  
 "Quitting Using Intensive Treatment Study (QUITS)"  
 PI: [name] and [name] ; UW-CTRI Grant:

the latter identifies the most robust interactions amongst subpopulations of a sample (groups of participants nested within levels of another predictor, which could include either a covariate or treatment condition). Candidate moderators of treatment effects on abstinence will include tobacco dependence, contextual factors such as household smoking, and biological variables such as sex and genotype. In the logistic regression analyses moderators will be evaluated with regards to their interactions with treatment main effects and interactions.

**Cost-Effectiveness:** Cost-effectiveness of key comparison treatments will be evaluated using methods recommended by the United States Panel on Cost-Effectiveness in Health and Medicine and consistent with our prior research in this area. We will: (1) measure all costs from the societal perspective; (2) convert cost estimates to a common year; (3) use a rate of 3% to discount future outcomes and costs to present value; (4) use QALYs as the outcome metric; and (5) conduct Monte Carlo sensitivity analyses. The proposed research will cost out all intervention component combinations that reflect significant main and synergistic interaction effects. We will determine net monetary benefit (NMB), cost per quit, and incremental cost-effectiveness ratios (ICERs). The components of NMB will be the added costs of the treatments and the monetized value of the QALYs added by the treatments. Using methods described by Stapleton, we will convert the increased effectiveness of the treatments from quits to added QALYs.

**Statistical Power for Primary Outcome:** Power was determined for effects that we prognosticated based upon prior data. Table 4 depicts predicted 52-week abstinence outcomes. We propose an abstinence rate for 12-week V treatment of 25%. This is comparable to that found in Koegelenberg for 12-week V-only treatment (28.8% at 24 weeks follow-up; abstinence rates tend to fall about 5 percentage points from 24 to 52 weeks post-TQD). This abstinence rate is higher than that produced by V-only in our recent clinical trial (19% abstinent at 52 weeks), but somewhat lower than the rates reported in the initial studies on V (52-week rates of about 30%; thus, we set the expected abstinence rate for 12 weeks of V at a mid-point (25%). Table 4 shows that we predict an increase in 52-week abstinence from 12 weeks of V alone (25%) to 34% for 12 weeks of V+P. We believe this increase of 9 percentage points is reasonable and somewhat conservative. It is midway between increases seen by Koegelenberg (15%) and Ramon et al., (5%, in 24-week *continuous* abstinence). Also, a 9 percentage point increase is somewhat less than the boost in abstinence seen with combination NRT vs. NRT monotherapy (36.5% vs. 23.4% at 5+ months as per the PHS Clinical Practice Guideline meta-analyses). In sum, we believe the estimated effect of the P adjuvant at 12-weeks duration seems reasonable and somewhat conservative.

**Table 4.** Predicted Biochemically Confirmed Abstinence Rates at 52-Weeks After the Target Quit Date

	V-only	V+ML	Marginals
12 Weeks of Medication	25.0% (78/312)	34.0% (106/312)	29.5% (184/624)
24 Weeks of Medication	32.0% (100/312)	44.9% (140/312)	38.5% (240/624)
Marginals	28.5% (178/624)	39.4% (246/624)	

Note: Koegelenberg et al., found abstinence rates of 65.1% (with multiple imputation) and 44% (with intent-to-treat) at 6-month follow-up with 12-weeks of V+P treatment. Thus, our predicted rates for V+ML may be conservative. Also, note that the new enrollment goal of 1250 does not divide evenly by 4=312.5, so we rounded down to 312 for the purposes of this chart.

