The predicted data would strongly implicate the additive effects of both 24-week duration and the P adjuvant as being necessary to achieve a marked increase in abstinence over standard V-based therapy. Of course, we might discover instead that a single treatment modification or enhancement confers as much benefit as the combination of the two components (e.g., 24-week V-only produces as much benefit as 24-week V+P). This finding would be welcome to the extent that it means that exceptionally strong results are obtained with the use of only one treatment enhancement, which would save money and perhaps reduce adverse events and burden.

**Statistical Power:** We computed power (via SAS PROC POWER) for the abstinence outcomes in Table 4, assuming  $p < .05$  and two-tailed tests. Power is .88 for the main effect for Duration (n's=625), and .97 for the main effect of Varenicline (V+P vs. V: n's=625). Moreover, power is  $> .99$  for the key hypothesis that the 24-week V+P combination will be superior to 12-weeks of V-only (n's=312). The N used clearly provides some room for error if the predicted outcomes are too sanguine. For instance, we noted above that some data suggest that the increase in abstinence seen with extended medication might be as small as 7%. The proposed N (1250) would permit detection of a 7 point difference with power = .80. Thus, the N proposed would provide good power to detect the proposed effects, and even effects that are modestly weaker, but still of public health significance.

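### The primary outcome is tested by factorial main effects and by arm-versus-standard contrasts, with no rule for which decides Aim 1, no error control across them, and a coding that leaves the main effects undefined

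*Combined protocol and SAP*

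**What the plan says.** Under Analytic Approach, Cessation, biochemically confirmed 7-day point-prevalence abstinence at 52 weeks "will be analyzed via two strategies". The first is a dummy-coded logistic regression with both factors and their interaction. The plan says that "main effects obtained with dummy coding in 2-factor designs are directly interpretable even in the presence of a significant interaction", provided that the interaction is in the model, and that the Duration term will reflect "the effects of 24- vs. 12-week treatment duration". The second strategy will "contrast each of the three enhanced varenicline treatments" with 12-week varenicline alone, to see whether any of them is superior.

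Specific Aim 1 relies on both: "The effects of these pharmacotherapy strategies will be reflected in main effects for both experimental factors, and in direct comparisons" of each enhanced arm with standard treatment.

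The Statistical Power paragraph gives power of .88 for Duration and .97 for the Adjuvant factor (625 per level). It also gives power above .99 "for the key hypothesis that the 24-week V+P combination will be superior to 12-weeks of V-only" (312 per arm). All are at two-sided .05.

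Control of experiment-wise error is stated for secondary abstinence outcomes only. No section ranks the two strategies, sets a testing order, divides alpha, or says what is concluded if they differ.

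**The concern.** Aim 1 asks whether the patch or the longer duration enhances varenicline, and each question can be answered twice on the same outcome. The main effect compares about 625 with 625. The matching arm contrast compares 312 with 312 and estimates something else: the effect of one change when the other is absent. With such different power, one test will often be significant and the other not. A report could then say that longer treatment enhances varenicline, or that this was not shown, and cite a prespecified primary analysis for either. The key-hypothesis label does not settle this, because that contrast changes both factors at once.

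Later work depends on the answer too. The cost-effectiveness section costs combinations with significant main or interaction effects, while the mediation section also models combinations that differ significantly from standard varenicline.

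There is a second gap. Under one ordinary reading of dummy coding, the main effects in the model are not those in the power calculation.

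**Working it through.** **Inputs.** Table 4, with 312 per arm:

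| | V-only | V+patch | Marginal |
|---|---|---|---|
| 12 weeks | 25.0% (78) | 34.0% (106) | 184/624 |
| 24 weeks | 32.0% (100) | 44.9% (140) | 240/624 |
| Marginal | 178/624 | 246/624 | |

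Tests are two-sided at .05. Power = Φ[(d − 1.96·SE0)/SE1], where SE0 = √[2p̄(1−p̄)/n] and SE1 = √[(p1(1−p1) + p2(1−p2))/n].

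**1. The plan's own power figures.** At 625 per level the formula gives .920 for Duration (stated .88), .983 for Adjuvant (stated .97), and .9996 for the key contrast at 312 per arm (stated >.99). The .88 is not reproduced. At 550 per level the formula gives .884 and .969, which match the stated pair. The stated values understate power for averaged main effects, and this does not affect the point.

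**2. Averaged Duration effect against its arm contrast.**
- Averaged, 184/624 vs 240/624: d = .0897, SE0 = .0268, SE1 = .0267. Power = Φ[(.0897 − .0526)/.0267] = .918.
- 24-week vs 12-week V-only, .32 vs .25: d = .07, SE0 = .03614, SE1 = .03603. Power = Φ[(.0700 − .0708)/.0360] = .491.
- 12-week V+patch vs 12-week V-only, .34 vs .25: power .694, against .983 for the averaged Adjuvant effect.

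**3. How often the two disagree.** From 1,000,000 simulated trials at Table 4 rates:

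| | Main effect significant | Arm contrast significant | Main effect only |
|---|---|---|---|
| Duration | .919 | .491 | .431 |
| Adjuvant | .984 | .695 | .289 |

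The reverse pattern for Duration occurs in .004 of trials. At least one factor is discordant in .53. With an effect-coded logistic Wald test in place of the marginal test, Duration disagreement is .427.

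**4. The model under 0/1 coding.** In logit p = b0 + b1·A + b2·D + b3·A·D, setting A = 0 gives b2 = logit p(24-week V-only) − logit p(12-week V-only). That is the arm contrast itself. On the exact Table 4 counts:
- b2 = ln(100/212) − ln(78/234) = .347; SE = √(1/100 + 1/212 + 1/78 + 1/234) = .178; z = 1.95; p = .052.
- With −1/+1 coding the Duration coefficient is the average of the two simple log-odds ratios, divided by 2: .201, p = .0009.

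So 0/1 coding gives no disagreement, but Duration power is .49 and Adjuvant power about .70.

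**5. False positives under a global null (common rate 25%).** At least one significant result:
- two averaged main effects: .098
- three arm contrasts: .126
- all five tests: .169

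The five-test figure is nearly the same at common rates of 19% and 30%. Adding the interaction gives about .19. Under 0/1 coding only the three arm contrasts are distinct, so the rate is about .12 to .13.

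**The case against.** The strongest reply is that the two strategies answer different, legitimate questions. One is the effect averaged over the other factor; the other is whether a given regimen beats standard care. Both are prespecified, and no section designates 24-week versus 12-week V-only as a test of the Duration factor. This stands in part. The estimands do differ, and the disagreement is mostly a gap in power: where only the Duration main effect is significant, the arm contrast points the same way in 97% of simulated trials. But Aim 1 names both analyses as evidence on the same yes-or-no question, and no rule says what follows when they part.

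A second reply is that the 43% does not come from the model as literally written. That is correct under 0/1 coding, so the figure is conditional. The averaged reading has good support in the Table 4 marginals, the 625-per-level power statement and the description of the Duration term. If it is rejected, the stated .88 and .97 lose their basis.

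A third reply is that Holm across two separately hypothesised factors in a Phase IV trial is a policy choice. It is, but it costs almost nothing here.

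A reader might also infer three stronger things that the documents do not support:
- That a promised 5% family-wise rate is exceeded more than threefold. The .05 appears as a power assumption, not as a family-wise promise, and the three contrasts alone already account for about .13 of the .17.
- That the strategies would give opposite findings. They differ in significance, almost never in direction.
- That the deciding analysis will be picked after unblinding. Both analyses are committed to; the plan leaves room for selective emphasis but does not show intent.

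**Conclusion.** The concern holds in conditional form. The plan tests one primary outcome by two unranked strategies, with no error control across them, and does not define its main effects clearly enough to say which test the first strategy performs.

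- **Averaged main effects:** about 43% of trials would show a significant Duration effect without a significant 24-week versus 12-week V-only contrast, and 29% the same for the Adjuvant pair. About 17% would have at least one significant result among the five tests if nothing worked.
- **0/1 coding with interaction:** no disagreement, but power of about .49 and .70 for effects that the plan believes are powered at .88 and .97.

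Either reading needs a change to the text. The figures assume Table 4 rates, 312 per arm, missing counted as smoking within those rates, and no covariate adjustment.

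**What to change.** In Analytic Approach, Cessation:

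1. Define each main effect as averaged over the other factor, by −1/+1 coding or an explicit marginal contrast, and correct the sentence on dummy coding.
2. Name the two main effects as the primary tests of Aim 1, with Holm across the two at .05. Alternatively, to keep the key hypothesis, test 24-week V+patch versus 12-week V-only first at .05 and go to the Holm pair only if it is significant.
3. Label the remaining arm contrasts as secondary estimates that do not override a main effect, and align Specific Aim 1 and the Statistical Power paragraph.

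The cost is wording only; no participants or data are affected. With averaged main effects, Holm takes Duration power from .918 to .917 and Adjuvant power from .984 to .982, with or without the key contrast first (power .9995). Step 1 is essential: Holm applied to the 0/1-coded terms would leave about .45 and .62.

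The downside is that a significant arm contrast alone no longer counts as a primary success (other than the key contrast, if it is placed first). With the key contrast first, neither main effect can be claimed if it fails.
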